8.10 Clinic Visit

The following activities are carried out during the clinic visit.:

- Provide the information sheet to the participant. Obtain informed consent verbally and via e-signature, and agreement with data privacy policy[sw1].
- Officially enroll participant.
- Administer the screening questionnaire (**Appendix 2**) to confirm participant eligibility
- Revisit the FRG and Decision Tree for Prescribing Mobility+, and use the additional information generated through the screening questionnaire to make a final decision on the appropriate giving-set tubing SKU (**Appendix 2**) for participants to begin the trial period with.
- Advise participant that operators (licensed to prescribe) may change the giving-set tubing SKU participants are to use, during the trial and or study days, if clinical and participant factors indicate this is needed (e.g. participant reflux may necessitate a change to slower flow rate, or participant finding feeding times too long may necessitate a change to a faster flow rate)
- Answer any queries
- Record the demographic data including calorie intake (**Appendix 3**).

	
Safety and Effectiveness of A Novel Enteral Feeding System: Prospective Study Protocol Page 23 of 49
	
NCT06173063

---	---	--

- Administer the participant perspectives baseline survey (**Appendix 4**) and quality of life survey (**Appendix 5**).
- Provide familiarization training as per **Appendix 11**.
- Provide necessary consumables.

8.11 Phone Communication

1. Pre-intervention phase – Trial days

Phone communication on **Trial Days 1; 3 and 5**: Participant is contacted by telephone to ensure the participant is becoming familiar with using the device including the most appropriate giving-set tubing SKU. (**Appendix 6**).

2. Intervention phase – Study days

- Phone communication - Study **Day 7**: Participant is contacted by telephone to ensure they are successfully and safely feeding with an appropriate tubing SKU, and check compliance and calorie intake (**Appendix 8**).
- Phone communication -Study **Day 14**: Participant is contacted by telephone to ensure participant is successfully and safely feeding with an appropriate tubing SKU, and check compliance and calorie intake. Operator also evaluates self-perceived wellbeing, mobility, wearing methods, and longer-term device use wishes (**Appendix 8**) Administer participant perspectives outcome survey, including question on QoL (**Appendix 7**)

Note: Regarding disposal – as per IFU, devices are disposed of alongside normal waste.

8.12 Training

Participants will be familiarized with how to use Mobility+ by the trained operator (**Appendix 11**).

Operators will log completion of familiarization training (**Appendix 12**). The operator advises the participant that the first 7 days of the use during the study are effectively a trial period to enhance comfort and familiarity with the system, before the 14-day intervention phase (Study Day 1 through Study Day 14) of the study.

Operators are to self-train in the use of Mobility+ (as detailed in DR010) and be trained in the execution of this Protocol by the sponsor, Rockfield Medical Devices (**Appendix 14**), before study execution. The sponsor will be available to provide continuous training to the operators throughout the duration of the study, as necessary.

Participants will be provided with the contact phone number of the Operator in case of questions or concerns.

8.13 Monitoring

PI will monitor participants experience of feeding with Mobility+ during the study as per schedule of phone communications in **Table 4** Study Schedule, and as outlined in **Appendices 6 and 9**. Should any adverse events or health threats become known to the operator via phone communications or otherwise, the operator will proceed to assess these as per **Appendices 9 and 10**. Furthermore, participant hospitalization for any reason during the trial days or study days will necessitate the ceasing of a participant's participation in this study (**Appendices 6 and 8**).

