3.0 Purpose

The purpose is to evaluate the safety and effectiveness of Mobility+ enteral feeding system via this initial post-market study (510k clearance number K222678) in adults, a subset of the intended use population. This evaluation will be conducted in a prospective, single arm, non-randomized clinical study.

Hypothesis and Objectives

The study hypothesis is that Mobility+ meets its intended use, safely. The objectives are to evaluate the below primary and secondary endpoints, through execution of this protocol:

Endpoint	Detail	How it will be measured
Primary: Safety and Effectiveness of Mobility+	Evaluate participants who have received familiarization training can use device, according to IFU, to allow delivery of liquid nutrition to their feeding tube, in a real-life setting (home), safely (i.e. can execute critical device use tasks to allow feeding, without serious adverse events) and with effectiveness (i.e. using Mobility+ for the majority or all of their feeding sessions i.e. two daily feeds, minimum)	Phone communication and checklist (Appendix8)

Secondary: Usability of Mobility+	Evaluate Participant perspectives on mobility, ease of use and tolerance, with their current feeding system(s) and Mobility+	Participant perspectives surveys: Baseline (Appendix 4) End of study (Appendix 7)
	Evaluate changes in participant Quality of Life (QoL)	QoL survey at baseline (Appendix 5) and QoL question at end of study (Appendix 7)
	Estimate if participants consume similar average volume (and kcals) of feed/day during the study, compared to baseline	Collect descriptive data on estimated average feed volume and kcals consumed at baseline (Appendix 3) and at end of study (Appendix 8)

The outcome will be presented in a study report.

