7.0 Definitions

Term	Description
User	Person interaction with medical device
Operator	Operators are study staff who have self-trained in the use of Mobility+ and who have received training in the execution of this Protocol by the sponsor, Rockfield Medical Devices. Study staff in this study comprise advanced nursing practitioners, registered dietitians, researchers and principal investigator.
Participant	Individual who is or becomes a participant in a clinical investigation, as a recipient of the investigational device. Note that 'participants' in this study are users of the device who are being enterally fed in clinical settings or who are feeding at home (as per Usability Engineering File DR010).
Investigational medical device	Medical device being assessed for clinical performance, effectiveness, or safety in a clinical investigation
Clinical effectiveness	Achievement of a clinically significant intended result in a defined portion of the target population when the investigational medical device is used within its intended uses and according to its instructions for use, as determined by documented scientific evidence
Malfunction	Failure of an investigational medical device to perform in accordance with its intended purpose when used in accordance with the instructions for use
Principal Investigator	Qualified person responsible for conducting the clinical investigation at an investigation site
Use error (ISO 14155:2020)	User action or lack of action while using the medical device that leads to a different result than that intended by the manufacturer or expected by the user. Note: Use error includes inability of the user to complete a task.
Adverse event (AE) (ISO 14155:2020)	Untoward medical occurrence, unintended disease or injury, or untoward clinical signs (including abnormal laboratory findings) in subjects, users or other persons, whether or not related to the investigational medical device and whether anticipated or unanticipated
Serious adverse	adverse event that led to any of the following

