effect (SAE)	
 a) Death b) Serious deterioration in the health of the subject, users, or other persons as defined by one or more of the following: 
 1) A life-threatening illness or injury, or 2) A permanent impairment of a body structure or a body function including chronic diseases, or 3) In-patient or prolonged hospitalization, or 4) Medical or surgical intervention to prevent life-threatening illness or injury, or permanent impairment to a body structure or a body function, c) Fetal distress, fetal death, a congenital abnormality, or birth defect including physical or mental impairment
Adverse device effect (ADE)	Adverse event related to the use of an investigational medical device.
Serious adverse device effect (SADE)	Adverse device effect that has resulted in any of the consequences characteristic of a serious adverse event
Unanticipated serious adverse device effect (USADE)	
Serious adverse device effect which by its nature, incidence, severity or outcome has not been identified in the current risk assessment
 
Note: Anticipated serious adverse device effect (ASADE) is an effect which by its nature, incidence, severity or outcome has been identified in the risk assessment

Serious public health threat	Serious public health threat, means an event which could result in imminent risk of death, serious deterioration in a person's state of health, or serious illness, that may require prompt remedial action, and that may cause significant morbidity or mortality in humans, or that is unusual or unexpected for the given place and time
Stock-Keeping Unit (SKU)	A Stock-Keeping Unit is a number (and sometimes letters) that is assigned to a product for the purpose of inventory management and ease or tracking

	
Safety and Effectiveness of A Novel Enteral Feeding System: Prospective Study Protocol Page 13 of 49
	
NCT06173063

---	---	---

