8.3 Participants

This is a first in human post-market clinical study to evaluate the Mobility+ system, being carried out following market approval (i.e., FDA clearance). 25 participants will be enrolled to ensure data can be obtained for 20 participants (the expected drop-out rate is estimated at ~20%), as this is considered appropriate for a post-market clinical study on a low-risk device and will add meaningful data to device risk management files. If more than 5 participants drop out, re-recruitment will aim to bring the sample size up to 20.

Recruitment will aim to obtain a mix of female and male participants who meet the inclusion criteria. Screening questions will be used by operators during the recruitment process to ensure participants are eligible (See **Appendix 1** and **Appendix 2**).

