7.0 Supplemental Outcome data gathered

The following supplemental Outcome Data was gathered (n=17).

Compliance and Effectiveness (n (%))	
Successfully and safely feed with Mobility+	17 (100)
Achieved use of Mobility+ for minimum 2 daily EN feeds	16 (94.1)

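### Hospitalisation ends participation and, when it is an SAE, fails the primary endpoint, but no rule carries that failure into the primary result

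*Protocol*

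**What the plan says.** - **Stopping rule.** Protocol 8.13: "participant hospitalization for any reason during the trial days or study days will necessitate the ceasing of a participant's participation in this study". It refers to Appendices 6 and 8 for this.
- **Primary endpoint.** Protocol 3.0 defines safe use as a participant who "can execute critical device use tasks to allow feeding, without serious adverse events". It does not restrict this to device-related events.
- **SAE definition.** Protocol 7.0 lists "In-patient or prolonged hospitalization" under serious deterioration in health. Adverse events count "whether or not related to the investigational medical device and whether anticipated or unanticipated".
- **Measurement.** Protocol 3.0 names the phone contact and the Appendix 8 checklist, completed on Study Days 7 and 14. The safety item there is one yes/no answer from the participant.
- **Drop-out.** Protocol 8.3 enrols 25 to obtain data on 20, and adds: "If more than 5 participants drop out, re-recruitment will aim to bring the sample size up to 20". It makes no distinction by reason for leaving.
- **Logging.** Protocol 8.7 has operators log withdrawals with reasons. Section 10.0 has the principal investigator record and assess SAEs and report serious matters within 24 hours.
- **Result.** SAP 3.0 gives 19 participants included. SAP 7.0, on n=17, gives "Successfully and safely feed with Mobility"+ as 17 (100).

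**The concern.** The event that ends participation can be the same event that fails the primary endpoint. Once a participant has stopped, the instrument that measures the endpoint is not completed, or is completed only in part. Neither document defines the primary analysis set or says how a participant stopped for an SAE is counted. A safety proportion built from Appendix 8 answers alone would therefore tend to leave out SAE failures, and the over-enrolment of five would absorb those losses without comment.

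Safety is half of the only primary endpoint, and the study hypothesis is that the device meets its intended use safely. If the proportion omits people stopped for SAEs, it describes those who stayed in the study and not those who used the device.

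**Working it through.** **1. What each admission leaves behind.** This sets the schedule (Protocol 8.8 and 8.11) beside the printed forms.

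| Time of admission | Appendix 8 answers | Scripted admission question |
|---|---|---|
| Trial Day 1 to the Trial Day 5 call | None | Appendix 6, Trial Day 5 |
| Rest of the trial period | None | None |
| Study Days 1 to 6 | Normally none | None |
| After the Study Day 7 call | Day 7; possibly Day 14 | Appendix 7, at the Day 14 contact |

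The Appendix 7 question looks back to the previous phone contact, so it reaches only to Study Day 7 if that call took place. Appendix 8 has no admission or SAE item, although 8.13 refers to it for hospitalisation. In the middle two rows an admission becomes known only by another route, such as a volunteered report.

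**2. The plan's own numbers.**
- Enrolment: 20 / (1 − 0.20) = 25. This reproduces, and it allows 25 − 20 = 5 losses before re-recruitment.
- SAP flow: 548 − 493 − 11 − 25 = 19. This also reproduces.
- Not accounted for in the SAP tables: 19 − 17 = 2.

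**3. Reported safety result** (exact Clopper-Pearson 95% intervals).
- As reported: 17/17 = 100% (80.5 to 100).
- All included, both missing participants counted as failures: 17/19 = 89.5% (66.9 to 98.7).
- All included, both counted as successes: 19/19 = 100% (82.4 to 100).

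**4. Illustrative planned worst case.** Suppose all five budgeted losses among 25 were SAE withdrawals.
- Those with data only: 20/20 = 100% (83.2 to 100).
- SAE withdrawals counted as failures: 20/25 = 80% (59.3 to 93.2).

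**5. How likely is any admission?** The documents give no admission risk. For an assumed risk p over the 21 days, the chance of at least one admission among 25 is 1 − (1 − p)^25. This is 0.40 at p = 2%, 0.72 at 5% and 0.93 at 10%. The chance of more than five admissions is below 0.001, 0.001 and 0.03 respectively.

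**The case against.** The case on the other side has real force.

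- **SAEs are not lost.** Sections 8.7 and 10.0 require them and the withdrawal reasons to be logged. On the wording of 3.0, a participant with an SAE does not meet the endpoint. This stands. The gap is only that the stated measure does not draw on those logs.
- **A hospitalised participant can still be seen at Day 14.** Appendix 7 asks about admission at that contact. This stands for admissions after the Day 7 call. A reader might infer that nobody in the Day 14 data can have failed by hospitalisation, and the documents do not support that.
- **Replacement is remote.** Re-recruitment needs more than five drop-outs, which admissions alone would rarely produce at the risks above. Section 8.3 neither defines drop-out nor says that recruits displace anyone from the denominator. A reader might infer that failures are routinely replaced, and the text does not say so.
- **A completers-only analysis is not specified.** Both documents are silent on the analysis set, so 20/20 illustrates one reading of the plan. SAP 7.0 is labelled supplemental, and n=17 also heads the baseline table in SAP 6.0, so it is not specific to Day 14 attendance.
- **Admission and SAE are not the same.** The rule in 8.13 covers any reason, while 7.0 requires serious deterioration in health. An elective admission may end participation without failing the endpoint.
- **No decision rule changes.** The study is single-arm, with no success threshold for the primary endpoint. This lowers the severity but does not make the reported proportion complete.

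**Conclusion.** The concern holds as a gap in counting. The stopping rule and the stated measurement together leave SAE failures outside the Appendix 8 answers, most clearly for admissions in the trial week, and no rule puts them back. It should be fixed before the safety proportion is relied on, but it does not invalidate the study.

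On the SAP's counts, the effect is at most the difference between 100% and 89.5%. In the illustrative planned worst case it is 100% against 80%, which needs all five losses to be SAE withdrawals.

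A reader might infer that the two participants missing from the n=17 tables were hospitalised. Nothing in the documents shows this, and 17/19 is a bound only. If neither of them used Mobility+, a denominator of device users would be 17 and the reported 100% would stand.

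**What to change.** Leave the clinical stopping rule unchanged and state how its consequences are counted, in Protocol 3.0 and 8.3 and in the SAP:

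1. Report the primary endpoint on all participants who used Mobility+. Show trial-day events separately from Study Days 1 to 14, because 8.1 assigns the assessment of safety and effectiveness to the latter.
2. Count any participant with an SAE, including an SAE-qualifying hospitalisation, as not meeting the endpoint. Take this from the SAE and withdrawal logs and split it by device-relatedness.
3. List admissions that are not SAEs separately, as withdrawals.
4. Add any re-recruited participants to the denominator without removing anyone.
5. Account for the two participants missing from the n=17 tables.
6. Reconcile the reference in 8.13 to Appendix 8 with what that sheet contains.

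The cost is a few sentences in each document and a re-count from records already required. The choice of denominator and time window has to be made openly, since it settles what the endpoint means. The headline figure may be slightly less favourable because it includes unrelated SAEs, and the relatedness split makes that visible.

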9.0 Risk Benefit

Risks associated with the investigational device and its use have been estimated in accordance with ISO 14971 prior to the development of this protocol. As part of ongoing risk management processes throughout the lifecycle of the device, and in line with SOP004, FMEA (Failure modes effects analysis) has been used to evaluate risks that may occur through use of the device and controls have been implemented to reduce risk to acceptable levels. Residual risks are deemed reduced as far as possible and are communicated in device labelling and other mitigation activities as per sponsor Risk documents. Benefits associated with the device outweigh risks. Risk benefit will be updated in risk management files (FMEA and Mobility+ Risk Management Report) following completion of the study report.

10.0 Safety Evaluation and Reporting

Safety evaluation and reporting will take place in line with Rockfield Medical Devices Quality Management System and SOPs on feedback and complaint management (SOP022 Customer Complaint Process Management).

The Principal Investigator (PI) undertakes to follow their institutes Institutional Review Board (IRB) policies regarding safety evaluation and reporting, and record AE's, SAE's, device deficiencies (including those which could lead to SADEs) and serious health threats, conduct an assessment on these, and report them to the IRB within 24 hours if the matter is considered serious, detailing the determination and action taken.

The PI also undertakes to report serious matters in a timely manner (within 24 hours) to the sponsor as per **Appendix 10**, following which the sponsor will review if the PIs assessment, determination, and actions are appropriate. The sponsor will also follow the sponsors relevant procedure on reporting (SOP022) and data outputs will be reviewed as part of SOP024.

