Appendix 5**QoL survey**

(Operator asks the Participant these questions)

Reference: Elfadil OM, Patel A, Abdelmagid M, et al. 1117929 - Mental Health Among Enteral Feeding Patients and Caregivers: Is Home Enteral Nutrition Overwhelming? Nutrition and Metabolism Research Oral Paper Session Abstracts. ASPEN Nutrition Science & Practice Conference: March 26-29, 2022 (Seattle, WA). JPEN J Parenter Enteral Nutr. 2022 Mar;46 (S1) <https://aspenjournals.onlinelibrary.wiley.com/doi/full/10.1002/jpen.2344>

Rate your quality of life	Excellent	Good	Neutral	Bad	Very Bad

Appendix 6
Phone Communication check sheet – Trial days

(Operator to use this check sheet to log tubing SKU and changes)

Tubing SKU check								
Trial Day 1: SKU that participant is using: 
 
 440mm RED 	700mm BLUE 	1000mm GREEN 	1900mm WHITE 	
 
					440mm RED 	700mm BLUE 	1000mm GREEN 	1900mm WHITE 
440mm RED 	700mm BLUE 	1000mm GREEN 	1900mm WHITE 					
Select one: 		Stay on this SKU 						
		Trial _____ SKU 						
Reason for changing: <hr/>								
Trial Day 3: SKU that participant is using: 
 
 440mm RED 	700mm BLUE 	1000mm GREEN 	1900mm WHITE 	
 
					440mm RED 	700mm BLUE 	1000mm GREEN 	1900mm WHITE 
440mm RED 	700mm BLUE 	1000mm GREEN 	1900mm WHITE 					
Select one: 		Stay on this SKU 						
		Trial _____ SKU 						
Reason for changing: <hr/>								

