Trial Day 5: SKU that participant is using: 
 
 440mm RED 	700mm BLUE 	1000mm GREEN 	1900mm WHITE 	
 
					440mm RED 	700mm BLUE 	1000mm GREEN 	1900mm WHITE 
440mm RED 	700mm BLUE 	1000mm GREEN 	1900mm WHITE 					
Select one: 		Stay on this SKU 						
		Trial _____ SKU 						
Reason for changing: <hr/>								
Have you been admitted to hospital in the last 5 days/during this trial period?		 Yes		 No				
Note to operator: Confirm you have reminded participant of the day they will begin the 14 day study period		 Yes		 No				

Appendix 7

Participant perspectives outcome survey

Participant perspectives of Mobility+ feeding system: Usability, mobility, and ease of use, including general end of study questions

(Operator asks the Participant these questions)

During use of the Mobility+ system, how do you find these activities?		Very Difficult	Difficult	Neutral	Easy	Very Easy
Moving from one room to another room						
Going up and down stairs						
Short walk (e.g., one block)						
Long walk (e.g., several blocks)						
Travelling in car/public transport						
Moderate intensity physical activities, such as:						

 - Moving a table - Pushing a vacuum - Bowling - Playing golf 						
Other daily activities (e.g., lifting or carrying groceries, household chores)						
Ability to sleep						
Socializing with friends/family						
During use of the Mobility+ system, how did you find working/studying or both? Please log N/A if participant does neither	Very Difficult	Difficult	Neutral	Easy	Very Easy	N/A
Note to operator: When scoring this questionnaire, assign points using the legend below.						
Very Difficult = 0 points, Somewhat Difficult = 1, Neutral = 2, Somewhat Easy = 3 and Very Easy = 4						
Thinking about your overall						

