		

How strongly do you agree with the following statement? I would like to use the Mobility+ again.

Strongly Agree	Somewhat Agree	Neutral	Somewhat Disagree	Strongly Disagree
				

If you would like to use Mobility+ again, how often would you like to use it?

Every Day	Every Week	Every Month
		

Think about your overall wellbeing if you used Mobility+ for SOME/ALL of your tube feeding needs, in the long term. How would your wellbeing be then, compared to now?

Much Better	Somewhat Better	About the Same	Somewhat Worse	Much Worse
				

Would you pay out of pocket for the Mobility+?

YES	NO
	

How did you choose to wear the Mobility+ system?

- Crossbody bag**
- Handbag**
- Backpack**
- In clothing**
- Clipped onto belt/clothing**
- Other (Detail):**

Appendix 8

Appendix 8 - Phone communication check sheet (Study Day 7 and 14) - (Operator asks the Participant these questions)

Day 7

Day 7			
Questions:	Answers:		
Day 7 Safety & Effectiveness Check			
Are you able to use Mobility+ to successfully and safely provide enteral feeding?	 YES  NO		
Day 7 Compliance & Calorie Intake Check			
Consider your feed intake over the last 3 days (i.e. Study day 4, 5, 6).			
Questions:	Answers:		
What volume of enteral nutrition did you consume on average per day (i.e. over 24 hr)?	Volume Mobility+mls		
How many hours did you typically infuse for, on average/day? hours minutes		
How many feedings did you intend to take using Mobility+ , on average / day?feedings		
How many feedings were you able to take using Mobility+ , on average / day?feedings		
What was the average volume of enteral nutrition that you consumed per feeding with Mobility+?mls		
What time of the day did you provide feedings with Mobility+?	Morning  Afternoon  Evening  Night-time 		
Operator facing question: On average, did the participant take at least two daily feeds with Mobility+? If no, why not?	 YES		
	 NO		
Day 7 Tubing SKU check			
Study Day 7:			
SKU that participant is using:			

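### Device deficiencies are to be recorded, but no call or survey asks about malfunction and no form counts devices used, so they are liable to be under-counted and no per-device rate can be computed

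*Protocol*

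**What the plan says.** Protocol 10.0 commits the principal investigator to "record AE's, SAE's, device deficiencies (including those which could lead to SADEs) and serious health threats". Section 8.3 supports the sample size partly on the ground that the study "will add meaningful data to device risk management files", and 9.0 adds: "Risk benefit will be updated in risk management files (FMEA and Mobility+ Risk Management Report) following completion of the study report". Section 7.0 defines a malfunction as "Failure of an investigational medical device to perform in accordance with its intended purpose when used in accordance with the instructions for use", but no form or analysis uses the term afterwards.

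The planned contacts after training are five telephone calls. For Trial Days 1, 3 and 5, section 8.11 gives the purpose as "Participant is contacted by telephone to ensure the participant is becoming familiar with using the device including the most appropriate giving-set tubing SKU". The form for these calls, Appendix 6, carries the instruction "Operator to use this check sheet to log tubing SKU and changes", with a free-text reason for any change. Its one safety item, on Trial Day 5, is "Have you been admitted to hospital in the last 5 days/during this trial period".

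On Study Days 7 and 14, Appendix 8 asks "Are you able to use Mobility+ to successfully and safely provide enteral feeding" as a yes/no item. It goes on to volumes, hours, feedings intended and achieved, and the tubing in use. The outcome survey in Appendix 7 is added on Day 14.

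SAP section 7.0 reports 17 (100) for feeding success and safety and 16 (94.1) for reaching the two-feed minimum. It gives no deficiency count.

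**The concern.** The device is used at home without supervision, and 8.11 lets used devices go out with household waste, so no planned inspection would reveal a failure. Section 11.1 names screening, surveys and telephone contacts as the sources for the study database. If those instruments do not ask about malfunction, the obligation in 10.0 depends on participants raising it themselves.

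The case most easily missed is a pouch that leaks or will not empty, is replaced, and does not stop the participant reaching two feeds that day. That participant can truthfully answer yes to the success item and meet the compliance criterion. An update of a failure-modes file would want to know how often this happens per device. The plan collects neither a solicited numerator nor a denominator for that figure.

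**Working it through.** **Planning figures.** The only planning figure is the enrolment target in 8.3. It reproduces: 20 / (1 − 0.20) = 25. The SAP percentage also reproduces: 16 / 17 = 94.1%. No figure is planned for device deficiencies, so the main check is a reading of each form.

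**What each form asks.**
- Appendix 6 (three calls): tubing in use, stay or change, free-text reason for a change, hospital admission on Day 5. Direct malfunction items: 0.
- Appendix 8 (two calls): the yes/no success item, volumes, hours, feedings intended against feedings achieved, and tubing. A reason is requested only if use averages below two feeds a day. The listed Day 7 reasons for changing tubing concern tolerance and feeding time. Direct malfunction items: 0.
- Appendix 7 (Day 14): activities, ease of use, gastrointestinal symptoms, admission, satisfaction and general questions. Direct malfunction items: 0.
- Appendix 9 classifies a deficiency once it is known. Appendix 10 lists the fields for reporting serious matters.
- No form records how many devices were used. Neither protocol Table 5 nor the SAP plans a deficiency count or rate.

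**Reach of the indirect prompts.** The feed questions look back three days before each Appendix 8 call (Study Days 4–6 and 11–13). That is 6 / 14 = 43% of study days, or 6 / 21 = 29% of all days of use, and none of the 7 trial days.

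**What a denominator would have allowed (illustration).** Assume one device per participant-day, because section 2.0 describes a 24-hour disposable system, and assume independent failures. With zero failures in m units, the upper limit of the exact two-sided 95% interval is 1 − 0.025^(1/m).
- Study days only: m = 17 × 14 = 238, limit 1 − 0.025^(1/238) = 1.54%.
- Trial and study days: m = 17 × 21 = 357, limit 1 − 0.025^(1/357) = 1.03%.
- If clustering within participants halved the effective number (an assumption), m = 238 / 2 = 119 and the limit is 1 − 0.025^(1/119) = 3.1%.
- Per participant: m = 17, limit 1 − 0.025^(1/17) = 19.5%. This is the proportion of people with any failure, a different quantity from the rate per device.

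**What reliance on spontaneous reports could cost (illustration).** Assume a true failure rate of 1% per device in 238 devices, so 238 × 0.01 = 2.38 failures are expected. Let s be the share reported. The chance that none is reported is (1 − 0.01 s)^238.

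| s | Expected reports | Chance of no report |
|---|---|---|
| 1 | 2.38 | 9% |
| 0.75 | 1.79 | 17% |
| 0.50 | 1.19 | 30% |
| 0.25 | 0.60 | 55% |

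The 1% rate and the values of s are assumptions; the documents give neither.

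**The case against.** The strongest reply is that the plan is not blind to device failure. Comparing intended with achieved feedings could expose a gross failure, as could the conditional request for a reason and the free-text reason for changing tubing. Participants also have the operator's telephone number (8.12), 8.13 covers adverse events and health threats that come to light by any route, and 10.0 brings in the sponsor's complaint procedure. That procedure and several figures, including the telephone decision tree and the deficiency chart, are not visible, so a prompt there cannot be ruled out. The text, however, ties the decision tree to tubing changes and the chart to classification. These routes stand, but they are indirect or passive and none supplies a device count.

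Several stronger readings are tempting and are not supported:
- That deficiencies were in fact under-counted. No true or recorded count is given; only a liability to under-count is shown.
- That the plan promises a failure rate to the risk files. Section 10.0 promises recording; 8.3 and 9.0 promise information for the risk files without naming deficiencies.
- That non-serious deficiencies go unrecorded because Appendix 10 covers serious matters. Section 10.0 separately requires device deficiencies to be recorded.
- That absence from SAP 7.0 means absence from reporting. That table is labelled supplemental, and protocol 3.0 sends the outcome to a study report.
- That 1.5% is a sharper version of 19.5%. The units differ.

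It is also fair to say that the device is cleared and described as low-risk, which bears on how serious the gap is.

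**Conclusion.** The concern holds as a gap in data capture. The plan requires device deficiencies to be recorded, but no scheduled instrument asks for them directly, devices used are not counted, and no analysis of deficiencies is specified. A failed and replaced device can pass through every form unnoticed, so 17 (100) does not exclude device failures. Equally, nothing in the documents shows that any occurred.

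The size of any under-count cannot be estimated from the documents. What can be sized is the information forgone: with solicited reports and a device count, zero failures would have bounded the per-device rate at about 1.5% over study days, or about 1.0% including trial days. Both figures rest on one device per participant-day, complete reporting and independence, and would be wider with clustering. They cover only the 17 participants with outcome data, although the SAP counts 19 as included. The gap should be corrected, but it does not invalidate the study's other results.

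**What to change.** For this protocol if it is reused, and for any further enrolment:
- At each of the five calls, ask whether since the last call any pouch, filling set or giving set has leaked, burst, disconnected, or failed to fill or empty, and if so how many, which part and which tubing SKU.
- At each call, also ask how many devices have been used since the last call.
- Provide a log that takes non-serious as well as serious deficiencies.
- Add one SAP table of deficiencies per device and per participant, for everyone who used a device, classified by Appendix 9. Give exact intervals for the per-participant proportion, and intervals that allow for within-participant clustering for the per-device rate.

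The SAP already reports results, so completed calls cannot be changed. For those data, list any deficiencies as spontaneous reports, state that they were not solicited, and do not present an absence of reports as a zero failure rate.

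The cost is a slightly longer call and one more table; for the existing data it is a few sentences in the report.
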